The study is a single-site, participant-blinded, pilot study for up to 60 patients in the Westlake dermatology clinic. Using the pen-like VAD, vibration will be applied with cotton on an anatomical site of one side (right or left) and without cotton on the same anatomical site on the other side. To fix cotton to the VAD, a cotton ball will be positioned at the tip of the VAD with placement into a nitrile glove (5). The VAD we are using for this procedure is the current standard of care and is not a novel device.

The anatomical sites were chosen in terms of sites with minimal subcutaneous fat and areas where patients have anecdotally reported discomfort with the VAD. The sites will be the lateral nasal wall, sub-malar region of the cheek, ear helix, lateral neck, and dorsal side of the forearm.

The order of the five anatomical sites and the order of conditions (VAD and VAD with cotton) will be randomized, and all possible orders will be placed into an envelope. One envelope will be randomly selected for each patient to determine the order of anatomical sites and order of condition for that particular patient. The patients will be blinded to what treatment is applied. For example, patients will be instructed to close their eyes or to look away from the application site.

There will be 10 total applications (VAD and VAD with cotton for five anatomical sites) each subject will undergo. Each application of the VAD will last for 20 seconds. Between each VAD application, there will be a delay of 10 seconds. After applying vibration to the same anatomical sites on the left and right side, patients will be asked which of the two treatments was preferred, which should take around one minute. To monitor participants for safety, participants will be encouraged to report any discomfort or adverse effects they experience during or after each vibration and after each VAD application, participants will be asked if they are ready to move on to the next one.

Before completion of the protocol, but after the informed consent, patients will be asked questions regarding their medical history. Additionally, before administering vibrations, patients will be trained to distinguish between small and large dowels, applying the minimum amount of pressure, while their eyes are closed to ensure accurate perception of the vibration.

Data will be patient reported and will be collected in a secure RedCap online database.

Study Timeline

Estimated time requirement of visit	Visit 1

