Patient Screening and Informed Consent	10 minutes
Data Collection	15 minutes
Anatomical site vibration (10)	15 minutes

Data to be Collected for your study

The study will collect sociodemographic information, including age, gender, and race, to understand the generalizability of data. Medical history data will encompass past medical conditions, history of prior procedures, and any previous use of vibration before injection. Patient chart will be looked at for the purpose of validating patient survey questions. Chronic pain history will be recorded, including the participant's relationship with a chronic pain specialist, current use and duration of pain medication, the specific medication used, and the

type, location, and duration of chronic pain. The presence, history, and location of neuropathy will also be documented. Lastly, the primary outcome variable will assess participant preference for each anatomical site, comparing the use of cotton versus no cotton.

Data Analysis Plan

As this is a pilot study, we are not able to conduct a power analysis. However, similar studies at UH using this same VAD have a similar target of up to 60 patients. A binomial test will be used to determine whether the proportion of participants preferring cotton differs significantly from the expected 50/50 baseline for each anatomical site. Additionally, Chi-Square Tests of Independence will be conducted to assess whether preferences for cotton versus no cotton vary based on participant characteristics, including chronic pain status, neuropathy status, or anatomical site. Qualitative data on the reason behind preference will be asked and independently categorized by at least two raters.

Risks to Research Participants

Minor discomfort may be experienced by patients from vibration for a few seconds per site. Additionally, there might be an anxiety due to potential discomfort. There will also be a risk of breach of confidentiality. Participants will be informed that they can withdraw from the study at any time without penalty.

Provisions to Protect the Privacy Interests of Research Participants

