Vibration tests will occur in private rooms. All collected data will be de-identified in RedCap, ensuring that no personally identifiable information is linked to study responses. Data will be securely stored in a password-protected, restricted-access database of REDCap, with access limited to authorized research personnel only. A coding system will be used, where a unique participant code is linked to each subject's data. Only authorized research personnel will have access to this code, and it will be securely stored separately from the study data in a linking log.

Potential Benefit to Research Participants

There is no direct benefit to research participants. Indirectly, if the use of cotton with vibration proves to be more comfortable for patients, it could provide a simple, cost-effective, and widely implementable solution for VAD use which optimizes patient comfort. This could be especially

beneficial for individuals with heightened pain sensitivity, such as those with chronic pain or neuropathy.

Withdrawal of Research Participants

Participants will be withdrawn from the study if they experience unexpected or intolerable discomfort that prevents them from completing the procedure. Additionally, participants may be withdrawn if they do not follow study instructions properly, which could compromise the integrity of the data collection process. If a participant withdraws before completing the procedure, their data will not be included in the study analysis. If a participant is withdrawn due to noncompliance or intolerable discomfort, their collected data will be discarded. Participants will be informed of their right to withdraw at any time without penalty.

Alternatives to Participation

The alternative to participation is not to participate.

Drugs or Devices

The pen-like vibratory anesthetic device which is the current standard of care in UH dermatology clinics and is not a novel device will be the main device used for this study on 5 anatomical sites each on the left and right side.

Additional Information

This VAD used is a current standard of care for dermatologic procedures, and this is not a novel device.

Community-Based Participatory Research

This is not community-based participatory research.

References

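### Discomfort and adverse effects are invited but have no planned record or report, and the data of anyone withdrawn for intolerable discomfort are discarded

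*Combined protocol and SAP*

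**What the plan says.** Study Procedures sets the exposure: "There will be 10 total applications (VAD and VAD with cotton for five anatomical sites) each subject will undergo". For safety monitoring it adds that "participants will be encouraged to report any discomfort or adverse effects they experience during or after each vibration", and that "after each VAD application, participants will be asked if they are ready to move on to the next one". It does not say that either response is written down. A general sentence in the same section reads "Data will be patient reported and will be collected in a secure RedCap online database", without naming variables.

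The section on data to be collected names sociodemographics, medical history, chronic pain history, neuropathy and the outcome: "the primary outcome variable will assess participant preference for each anatomical site, comparing the use of cotton versus no cotton". The Data Analysis Plan consists of binomial and chi-square tests of preference, plus one further item: "Qualitative data on the reason behind preference will be asked and independently categorized by at least two raters". Neither section mentions discomfort reports, adverse effects, pauses, or the point of and reason for stopping.

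Withdrawal of Research Participants requires withdrawal when discomfort prevents completion, and then states: "If a participant is withdrawn due to noncompliance or intolerable discomfort, their collected data will be discarded". Participants who leave early of their own accord are left out of the analysis.

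**The concern.** Comfort is the question the trial asks. The Background states that the study will settle whether cotton improves it, the sites were chosen partly because patients had reported discomfort there, and discomfort comes first in the section on risks. A volunteered complaint, or a stop during a particular application, bears on that question because it belongs to one condition at one site.

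Two features of the plan act together. Reports have no named place in the data, even for people who complete all ten applications. For people who stop because they cannot tolerate the device, a stated rule removes whatever was collected. The second feature is an instruction to delete, not just missing detail, and it acts on the most severe events. The section on potential benefit expects cotton to help people with heightened pain sensitivity most. If such people also stop more often, which is an inference the documents do not state, the rule falls hardest on them.

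The visit is single, so information not logged during it cannot be recovered later.

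**Working it through.** The plan gives no discomfort, adverse-effect or withdrawal rate and no power calculation, so there is no figure of its own to reproduce. The check is a reading of the sections against each other, followed by an illustration of size.

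**1. Following a report through the plan.**

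| Event | Invited or foreseen? | Named variable? | Planned analysis or report? | Kept? |
|---|---|---|---|---|
| Discomfort or adverse effect, participant completes | Yes (Study Procedures) | None | None | Not specified |
| Answer to readiness question | Yes (Study Procedures) | None | None | Not specified |
| Intolerable discomfort, participant withdrawn | Yes (Withdrawal) | None | None | Collected data discarded |
| Preference by site | Yes | Yes | Binomial and chi-square tests | Yes, completers |
| Reason for preference | Yes (Data Analysis Plan) | Only in the analysis plan | Rater categories | Yes, completers |

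Only the last two rows reach a result. Both concern a left/right pair, not a single application.

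**2. Ceiling on exposure.** Up to 60 participants × 10 applications = 600 applications, or 60 × 5 = 300 per condition. This is a maximum, because enrolment is up to 60 and any stop lowers it.

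**3. Size of what the discard rule removes (assumed counts).** For x withdrawals for discomfort among n = 60, the exact (Clopper-Pearson) 95% limits are: lower = 2.5% quantile of Beta(x, n − x + 1); upper = 97.5% quantile of Beta(x + 1, n − x). The lower limit is 0 when x = 0.

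| x of 60 | Proportion | Exact 95% CI |
|---|---|---|
| 0 | 0% | 0% to 6.0% |
| 1 | 1.7% | 0.04% to 8.9% |
| 3 | 5.0% | 1.0% to 13.9% |
| 6 | 10.0% | 3.8% to 20.5% |

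All 60 are assumed to be enrolled and to receive at least one application. With x = 3, the retained data hold 60 − 3 = 57 people, none of them withdrawn.

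**4. What such counts can show.** If 3 withdrawals all arose under one condition, the exact two-sided binomial p is 2 × 0.5³ = 0.25. The counts therefore support description, not a test.

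**5. Room in the session.** Ten 20-second applications take 200 s, nine 10-second gaps take 90 s, and five preference questions at about one minute take 300 s, a total of 590 s. The timeline allows 15 minutes = 900 s for the vibration block, which leaves about 310 s, or 31 s per application, if the dowel training falls outside that block.

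**The case against.** The strongest reply is that silence is not prohibition. The list of data to be collected is not exhaustive: the reason for each preference is absent from it yet appears in the Data Analysis Plan. The general REDCap sentence could also be taken to cover safety reports. This stands. A reader might infer that reports will be heard and never stored, so that 600 applications yield no safety observation. The documents do not support that. They show that recording is unspecified, and 600 is only a ceiling.

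Second, paired preference is itself a relative measure of comfort, and the reasons given may attribute discomfort to one condition. This also stands, so it would be too strong to say that the trial learns nothing about tolerability by condition. Preference is only relative, however. A participant can prefer cotton when both applications were uncomfortable, or when neither was. The reasons come from completers and relate to a pair.

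Third, the stated purpose of the reports is monitoring during short applications of a standard-of-care device with minor discomfort expected, and the objectives speak of preference. That argues for light recording and against a formal endpoint. It does not explain why data from people who could not tolerate the procedure are deleted.

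Fourth, adding a yes/no discomfort question after each application would be a new elicited item asked before the preference answer, and could prime the primary outcome. This is right, and it shapes the remedy.

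Finally, the condition in progress at a stop also reflects site, order and accumulated exposure, so a handful of stops cannot establish a cause.

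**Conclusion.** The point holds in this form: the plan invites discomfort and adverse-effect reports, provides no variable, analysis or report for them, and discards the data of participants withdrawn for intolerable discomfort. The planned preference analysis can still run. What has no planned route to a result is the incidence of discomfort, adverse effects and discomfort withdrawals by condition and site.

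The size cannot be fixed from the documents. The 5.0% illustration rests on an assumed 3 withdrawals among 60 enrolled; over 0 to 6 withdrawals the proportion runs from 0% to 10.0%.

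Two stronger readings should be avoided. A reader might set 5.0% against 0 of 57 retained and treat the latter as a biased estimate. It is a structural zero, since completers cannot have been withdrawn, and the plan nowhere proposes to report it. A reader might also infer that withdrawals would be hidden altogether. Enrolled-minus-analysed numbers could still be given, and applying the rule requires staff to know why someone was withdrawn. What that would not give is the condition and site.

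The change should be made before enrolment. It is inexpensive, and the loss falls on evidence close to the trial's stated aim.

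**What to change.** **Data to be collected.** Add a staff-completed REDCap log, tagged with site, side and condition, that records:
- any discomfort or adverse effect the participant volunteers;
- the answer to the existing readiness question;
- any stop, with its reason.

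Do not add a new elicited discomfort question before the preference answer.

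**Withdrawal of Research Participants.** Change the data rule so that these entries and the reason for withdrawal are kept, as consent allows. This concerns data retention only; the criteria for withdrawing someone are untouched.

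**Data Analysis Plan.** State that counts will be reported by condition and site, descriptively and without a test, in everyone who received at least one application. Show discomfort withdrawals by the condition and site in progress.

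**Cost.** The log takes a few seconds of entry per application, which the vibration block appears able to absorb. The consent wording may need to be aligned with the retention change. The published discomfort rate may look less favourable. No extra visit or procedure is needed.

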Improving Patient Comfort of Vibratory Anesthetic Devices with a Cotton Dampener

01/29/2025

NCT06916468

Objectives

The study aims to determine the effectiveness of cotton as a dampener for vibratory anesthetic devices (VADs) for dermatologic patients. It will compare patient preferences for VAD use with and without cotton across different anatomical sites and identify factors, such as chronic pain or neuropathy status, that may influence these preferences. Finally, the study seeks to generate preliminary data to inform potential modifications to VAD use, optimizing patient comfort in dermatologic procedures.

Background

Vibratory anesthetic devices (VADs) decrease pain associated with anesthetic, steroid, or botulinum toxin injection in dermatology patients through the application of vibratory stimulation on targeted anatomical site [1,2,3]. While VADs are effective at reducing injection pain, a number of factors influence their adoption by injectors. One factor is patient comfort [4]. Anecdotally, some patients have reported discomfort with VADs used before dermatologic procedures. As this may be influencing the utilization of VADs in dermatological procedures, further investigation into patient comfort with VAD is necessary. This study will determine whether utilizing cotton balls as a dampener is effective in improving patient comfort with VAD use.

Inclusion and Exclusion Criteria

The study will include potential participants based on their ability to provide informed consent and complete the study, while excluding those with skin conditions, sensitivities at testing sites, or allergies to nitrile gloves or cotton.

Inclusion Criteria	
1.	Age range: from 18+
2.	Dermatologic patients at Westlake Clinic
3.	Consent: Must provide informed consent to participate in the study.
4.	Availability: Able to complete the entire study session, which includes testing all sites in a single session

Exclusion Criteria	
1.	Broken skin or known peripheral neuropathy on anatomical site of vibration.
2.	Allergies: Known allergy or sensitivity to nitrile gloves or cotton
3.	
4.	

Study Design

The overall study design is a single-site, one-visit, participant-blinded, pilot study for up to 60 patients in the Westlake dermatology clinic.

Study Procedures

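### The plan asks whether cotton improves comfort in general but tests it against 50/50 only site by site; one added participant-level test would answer the general question

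*Combined protocol and SAP*

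**What the plan says.** The aim is put at two levels. The Objectives open generally: "The study aims to determine the effectiveness of cotton as a dampener for vibratory anesthetic devices (VADs) for dermatologic patients". The Background repeats this: "This study will determine whether utilizing cotton balls as a dampener is effective in improving patient comfort with VAD use". Neither sentence names a site. The Objectives then turn to sites, "It will compare patient preferences for VAD use with and without cotton across different anatomical sites", and describe the purpose as preliminary: "the study seeks to generate preliminary data to inform potential modifications to VAD use".

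Under Study Procedures, each participant is tested at five sites, with cotton on one side and without on the other. At each site "patients will be asked which of the two treatments was preferred". The study is a "pilot study for up to 60 patients in the Westlake dermatology clinic".

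The section on data to be collected states that "the primary outcome variable will assess participant preference for each anatomical site, comparing the use of cotton versus no cotton". The Data Analysis Plan follows this with a binomial test of whether the proportion preferring cotton "differs significantly from the expected 50/50 baseline for each anatomical site". It adds chi-square tests of whether preference varies with chronic pain, neuropathy or site. It describes no test that combines the sites, and does not say what is concluded about cotton in general if some sites are significant and others are not.

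**The concern.** A reader of the Objectives and Background expects one answer on whether cotton helps. The Data Analysis Plan delivers five, none ranked above the others. If cotton is moderately preferred everywhere, chance alone will often make some sites significant and leave others not, and the plan then gives no basis for a general statement in either direction.

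Two improvised answers are possible once the data are in. One is to claim general benefit from any significant site. The other is to pool all the answers as if they came from different people. The second is not valid, because each participant contributes five answers.

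**Working it through.** **1. Question against test**

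| Question | Planned test |
|---|---|
| Is cotton preferred at a given site? (primary outcome) | Binomial test against 0.5 at that site |
| Does preference differ between sites? (Objectives) | Chi-square by site |
| Is cotton preferred overall? (Objectives, Background) | None |

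The chi-square by site cannot fill the third row. If cotton were preferred equally at every site, its null hypothesis would be true.

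**2. Inputs**

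From the documents: five sites, at most 60 participants, null value 0.5. The plan gives no power calculation, so it has no figure to reproduce. Assumed: two-sided 0.05, exact binomial test, 60 completers, true preferences as stated below, and an exchangeable latent-normal correlation between a person's sites of 0, 0.3 or 0.8. Triplets are in that order. Correlated settings and combined-test results come from 20,000 simulated trials per setting.

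**3. One site**

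The smallest r with 2·P(X ≥ r | 60, 0.5) ≤ 0.05 is 39 (65%). P(X ≥ 39 | 60, 0.5) = 0.01367, so the two-sided size is 0.0273. Power, P(X ≥ 39 | 60, p), is 0.257 at p = 0.60, 0.838 at 0.70 and 0.970 at 0.75.

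**4. How often the five tests disagree, 60% at every site**

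Independent sites, with per-site power 0.2568:
- all five significant: 0.2568^5 = 0.001
- none: (1 − 0.2568)^5 = 0.227
- mixed: 1 − 0.001 − 0.227 = 0.772

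At correlation 0.3 and 0.8, mixed results occur in about 69% and 49% of trials, and no site is significant in about 31% and 46%.

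**5. One participant-level test**

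Let m_i be participant i's proportion of sites preferring cotton, with mean m and standard deviation s. The t-test is t = (m − 0.5)/(s/√60) on 59 degrees of freedom. With complete data, the intercept-only logistic GEE with robust standard error (n/(n−1) correction) is ln[m/(1 − m)] divided by s/[√60·m(1 − m)], on the same reference.

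| True preference | GEE rejects | At least one site significant for cotton |
|---|---|---|
| 50% everywhere | 4.5/4.6/4.2% (for cotton: 2.1/2.3/2.1%) | 6.5/6.4/4.9% |
| 60% everywhere | 93/72/45% | 78/69/54% |
| 70% everywhere | 97–100% | 98–100% |

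The t-test has type I error of about 5%.

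**6. False positives from the site tests**

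At n = 60 with independent sites: 1 − (1 − 0.01367)^5 = 0.067 for cotton, and 1 − (1 − 0.0273)^5 = 0.129 in either direction. Over the three correlations this is about 5–7% and 10–13%. For n from 30 to 60 with independent sites, the figure for cotton runs from 4.9% (n = 32) to 11.6% (n = 51). At n = 51 the per-site size is 0.0489, so either direction gives 1 − (1 − 0.0489)^5 = 0.222.

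**7. Simple pooling**

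A binomial test on all 60 × 5 = 300 answers has type I error of about 13% at correlation 0.3 and 27% at 0.8.

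**8. Where the combined test does worse**

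- 75% at one site, 50% elsewhere: 41/25/15%, against 97% for that site's own test.
- 70% at two sites: 80/56/33%, against 84% for each site's own test. Two or more sites significantly favour cotton while the combined test is not significant in about 9/22/42% of trials.
- 70/70/30/30/50%: the average is 250/5 = 50%, so the combined null is true and its rejection rate of about 5% is simply its error rate.
- 75/75/40/40/50%: the average is 280/5 = 56%, and power is about 57/37/22%.

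**The case against.** The strongest reply is that objective, outcome and test already agree at site level. The Objectives go straight from effectiveness to preferences across sites, the primary outcome is preference at each site, and the binomial tests address exactly that. No sentence asks for an average over nose, cheek, ear, neck and forearm, and the study is a pilot. Much of this stands. It is why the site tests should stay primary and why this is an improvement and not a correction. It does not remove the gap, because two sentences still promise a finding about cotton in general.

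It can also be said that the size depends on an assumed 60% preference. That is true: at a common 70%, the combined test and at least one significant site are both almost certain. Nor is the combined test always the more powerful. At 60% and correlation 0.8 it has 45% power against 54% for an any-site rule, though with 2.1% instead of 4.9% error in favour of cotton.

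A reader might infer three stronger points that the documents do not support:
- That the site tests are wrong. They match the stated primary outcome.
- That false positives are the main danger, citing 1 − 0.95^5 = 22.6%. At n = 60 the exact test gives 10–13% in either direction. A figure near 22% arises only at an unfavourable number of completers such as 51, with independent sites.
- That the unstated significance level, the unstated sidedness or the lack of a rule for a participant with no preference is itself a fault. These are missing details. Testing for a difference already reads as two-sided, and the question put to participants reads as a choice between two.

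**Conclusion.** The point holds as a low-cost improvement. That no planned test answers the general question follows from the text alone. How much this matters depends on the assumed level, preference and correlation: with a moderate, uniform preference near 60% a mixed or empty set of site results is the usual outcome, and with 70% or more the added test changes little. The documents do not support calling the site tests invalid, or downgrading their results to exploratory.

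**What to change.** Add to the Data Analysis Plan:

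1. The five site binomial tests remain the primary analysis, each reported with an exact 95% confidence interval.
2. For the general question, one participant-level test of whether the average proportion preferring cotton differs from 50%, two-sided at 0.05, with a 95% confidence interval. Use either an intercept-only logistic GEE clustered by participant, with robust standard error and a t reference, or a one-sample t-test on each participant's proportion. Name one of them before the data are seen.
3. The answers are not pooled in a simple binomial test.
4. Any general statement that cotton is preferred rests on the test in 2. If that test is not significant, significant sites, however many, are reported as site-specific primary results, with a note that five tests were done without adjustment.
5. The site results are always shown beside the combined test.

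The cost is a few sentences of wording; no data, visits or participants are added. The drawback is that the combined test concerns an average. It can miss an effect confined to one or two sites, and effects in opposite directions offset each other, so item 5 is essential.

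### The chi-square test of preference by site treats five answers from the same patient as answers from different people, and the unit of analysis for chronic pain and neuropathy is not stated

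*Combined protocol and SAP*

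**What the plan says.** The Data Analysis Plan tests, with chi-square tests of independence, whether "preferences for cotton versus no cotton vary based on participant characteristics, including chronic pain status, neuropathy status, or anatomical site". It names no matched, clustered or repeated-measures method.

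Other sections fix the structure of the data:

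- Study Procedures, exposure: "There will be 10 total applications (VAD and VAD with cotton for five anatomical sites) each subject will undergo".
- Study Procedures, outcome: "After applying vibration to the same anatomical sites on the left and right side, patients will be asked which of the two treatments was preferred". This gives one binary answer per site per patient.
- Inclusion Criteria: a patient must be "Able to complete the entire study session, which includes testing all sites in a single session".
- Withdrawal of Research Participants: "If a participant withdraws before completing the procedure, their data will not be included in the study analysis".
- Study Procedures, size: a "single-site, participant-blinded, pilot study for up to 60 patients in the Westlake dermatology clinic".

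The sentence on the primary binomial test says that it is run by site: it asks whether the proportion preferring cotton "differs significantly from the expected 50/50 baseline for each anatomical site". The chi-square sentence has no such phrase.

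**The concern.** A chi-square test of independence assumes that the site columns hold different people. Here all five columns hold the same people. The test therefore uses the wrong variance for a difference between sites. This is the only planned test of whether preference differs from site to site.

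The chronic-pain and neuropathy tests raise a separate question. These factors vary between patients, so one answer per patient gives a valid test. The plan does not say whether the tests are run at each site or on one table of up to 60 × 5 = 300 answers. Listing site beside the two patient-level factors makes a dataset with one row per answer a plausible reading. In that table each patient would count five times, and the error would be in the opposite direction: too many false positives. The Objectives name chronic pain and neuropathy as factors to be identified, so the choice should not be left until the data are in hand.

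**Working it through.** **Inputs from the documents.** Five sites, one binary answer per site, every analysed patient complete, at most 60 patients. The plan states no power, significance level, correlation or preference rate, so it has no figure to reproduce.

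**Assumptions.** Nominal two-sided 5%; 60 patients; within-patient correlation rho of 0.1, 0.2, 0.3 and 0.5, with 0 and −0.1 as checks.

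**Site test, theory.** Suppose preference is p at every site and any two answers from one patient have correlation rho. Differences between site totals then have variance proportional to n·p(1−p)(1−rho). The chi-square test divides by n·p(1−p), so its statistic behaves as (1−rho) times a chi-square on 4 degrees of freedom:

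true size = P(χ²₄ > 9.488/(1−rho))

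At rho 0.3 this is P(χ²₄ > 13.55) = 0.9%.

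**Pooled patient-level test, theory.** Five answers per patient inflate the variance by 1 + 4·rho:

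true size = 2·[1 − Φ(1.96/√(1+4·rho))]

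At rho 0.3 this is 2·[1 − Φ(1.96/√2.2)] = 2·[1 − Φ(1.32)] = 18.6%.

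**Simulation.** 20,000 to 40,000 trials per setting of 60 × 5 binary answers came from a shared latent normal variable, set so that the average correlation of the binary answers equals rho. Size of the site test assumes 62% preferring cotton at every site. Power assumes site rates of 75/70/62/55/50%.

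| | rho 0.1 | 0.2 | 0.3 | 0.5 |
|---|---|---|---|---|
| Site chi-square, size, theory | 3.2% | 1.8% | 0.9% | 0.1% |
| Site chi-square, size, simulated | 3.1% | 1.9% | 1.0% | 0.1% |
| Site chi-square, power | 0.76 | 0.75 | 0.75 | 0.73 |
| Cochran's Q, power | 0.81 | 0.86 | 0.91 | 0.98 |
| Pooled patient-level test, size, theory | 9.8% | 14.4% | 18.6% | 25.8% |
| Pooled patient-level test, size, simulated | 10% | 15% | 19% | 26% |
| Pooled, continuity-corrected, simulated | 8% | 12% | 16% | 23% |

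Over the same values of rho:

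- Cochran's Q has size 4.7 to 4.9%.
- Site-by-site 2×2 tests, with 15 of 60 patients having the characteristic, hold 4.7 to 5.4% each.
- A rank-sum test on each patient's count of sites preferring cotton holds 4.3 to 5.0%.
- With 6, 15 or 30 of 60 patients having the characteristic and 50 to 75% preferring cotton, the uncorrected pooled test runs at 9–11% (rho 0.1), 18–20% (0.3) and 26–27% (0.5).

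A second simulation with a beta-binomial generator and overall preference of 50% or 70% gave the same direction and size: at rho 0.3 and 60 patients, site chi-square 0.9 to 1.0% and pooled test 18.8 to 20.2%.

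**Boundary cases.** At rho 0, with the same site rates, power is 0.76 for the chi-square and 0.75 to 0.76 for Cochran's Q. At rho −0.1 both effects reverse: the site chi-square has size 7.1% and the pooled test 1.1%.

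**The case against.** The strongest reply is about weight. The study is a pilot without a power analysis, the chi-square tests are additional to the primary binomial tests, and those use one answer per patient and are sound. With positive correlation the site test produces no excess false positives, only lost power, and at rho 0 not even that. The site objective can be read as cotton versus no cotton at each site, which the binomial tests deliver. The plan never commits to pooling, and since the primary outcome is defined by site, site-by-site tables are a natural reading for chronic pain and neuropathy.

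Most of this stands as a limit on the size of the point. The pooled error rates apply only if the answers are pooled. No single equivalent sample size can be given: under the assumed rates and rho 0.3 the chi-square needs about 82 patients to match Cochran's Q with 60, but other assumptions give other figures. With a 12-point spread in site rates (68 to 56%) at rho 0.3, power is 0.10 against 0.26, inadequate for both tests. With 30 patients and the original rates it is 0.33 against 0.57.

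None of it rescues the test. The plan itself asks whether preference varies by site, and it answers with a method for independent groups. A pilot that reports formal tests still needs ones that fit its design. Cochran's Q loses essentially nothing at rho 0 and gains power at every positive rho tried.

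**Conclusion.** The concern holds. The mismatch between the site test and the design follows from the documents alone. Its size depends on rho and the site rates, which the documents do not give. For rho 0.1 to 0.5 with 60 patients, the nominal 5% site test has true size between 3.1% and 0.1%. Its power under the assumed site rates is 0.76 to 0.73, against 0.81 to 0.98 for Cochran's Q. A null site result could therefore reflect the choice of test.

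The chronic-pain and neuropathy half is an omission, not a demonstrated error. The wording permits a test that holds about 5% and another that runs at about 10 to 26% over the same range of rho, and nothing in the text rules out the second. The primary conclusions at each site are not touched. This should be corrected before analysis, but it does not put the trial's main result in doubt.

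**What to change.** - **Site.** Replace the chi-square with Cochran's Q, which suits the complete blocks that the withdrawal rule produces, or with the site term of a GEE or mixed logistic model clustered on patient. Stop calling site a participant characteristic.
- **Chronic pain and neuropathy.** State one unit of analysis. Acceptable choices are one value per patient (the number of the five sites at which cotton was preferred) with a rank-sum or exact test; patient-level terms in the same clustered model; or a separate 2×2 test at each site. The count is simple but hides an effect that differs by site. Whichever is chosen, rule out a table that pools the five answers as if they were independent.
- **Small groups.** Known peripheral neuropathy at a vibration site is an exclusion criterion, so the neuropathy group may be small. With 6 of 60 patients and 75% preferring cotton, the smallest expected cell in a site-by-site table is 6 × 0.25 = 1.5, and the uncorrected chi-square there had a simulated size of 3.3%. Specify an exact test for such tables.

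The cost is a few sentences in the Data Analysis Plan and a few lines of code, with no new data and no extra patients. It should be written down before the data are analysed.
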